4.5.4 Use in Pregnancy

If a subject inadvertently becomes pregnant while on treatment with pembrolizumab, the subject will immediately be removed from the study. The site will contact the subject at least monthly and document the subject's status until the pregnancy has been completed or terminated. The outcome of the pregnancy will be reported to the PI and to Merck without delay, and within 24 hours to the PI and within 2 working days to Merck if the outcome is a serious adverse experience (e.g., death, abortion, congenital anomaly, or other disabling or life-threatening complication to the mother or newborn).

The treating investigator will make every effort to obtain permission to follow the outcome of the pregnancy and report the condition of the fetus or newborn to the PI. If a male subject impregnates his female partner the study personnel at the site must be informed immediately and the pregnancy reported to the PI and to Merck and followed as described above and in Section 7.3.5.2

It is unknown whether pembrolizumab is excreted in human milk. Since many drugs are excreted in human milk, and because of the potential for serious adverse reactions in the nursing infant, subjects who are breastfeeding are not eligible for enrollment.

4.6 Duration of Trial

4.6.1 Duration of Therapy

Patients will be treated with 3 cycles of pembrolizumab (9 weeks) followed by AVD for 4-6 cycles (4-6 months) followed by pembrolizumab consolidation (selected patients) for up to 2 total years of pembrolizumab.

4.6.2 Duration of Follow Up

Once patients are off treatment for any reason, they will have a final off-treatment visit approximately 30 days post-last dose of study therapy. Thereafter, they will be followed with at least one clinic visit every 3 months for up to 2 years from end of treatment. Patients removed from treatment for unacceptable adverse events will be followed until resolution or stabilization of the adverse event.

For patients who undergo allogeneic stem cell transplant (SCT) within 2 years of study treatment, transplant parameters and adverse events will be recorded as detailed in section 4.6.3.

4.6.3 Subject Withdrawal/Discontinuation Criteria from Treatment and/or Overall Study

Subjects may withdraw consent at any time for any reason or be dropped from the trial at the discretion of the investigator should any untoward effect occur. In addition, a subject may be withdrawn if enrollment into the trial is inappropriate, the trial plan is violated, or for administrative and/or other safety reasons. Specific details regarding discontinuation or withdrawal are provided in Table 4.1.

A subject must be discontinued from the trial for any of the following reasons:

- Patient voluntarily withdraws from treatment (follow-up permitted)
- The subject or legal representative (such as a parent or legal guardian) withdraws consent (no follow-up permitted).
- Confirmed radiographic disease progression
- Note: For unconfirmed radiographic disease progression, please see Section 5.1.6
- Unacceptable toxicity/adverse experiences as described in Section 4.4
- Intercurrent illness that prevents further administration of treatment
- Investigator's decision to withdraw the subject (i.e. continuation not in the patient's best interest)
- The subject has a confirmed positive serum pregnancy test
- Patient develops a second malignancy that requires treatment which would interfere with this study
- Noncompliance or inability to comply with trial treatment or procedure requirements
- The subject is lost to follow-up
- Administrative reasons

The End of Treatment and Follow-up visit procedures are listed in Section 5 (Protocol Flow Chart). After the end of treatment, each subject will be followed for 30 days for adverse event monitoring (serious adverse events will be collected for 90 days after the end of treatment as. Subjects who discontinue for reasons other than progressive disease will have post-treatment follow-up for disease status until disease progression, initiating a non-study cancer treatment, withdrawing consent or becoming lost to follow-up. After documented disease progression each subject will be followed by telephone for overall survival until death, withdrawal of consent, or the end of the study, whichever occurs first.

Patients who undergo allogeneic transplant will be monitored for adverse events. For subjects who have an allogeneic SCT within 24 months of last study treatment, transplant parameters will be collected and specific events will be collected for 18 months from the date of the allogeneic transplant to include graft-versus-host-disease (acute and/or chronic), veno-occlusive disease, febrile syndrome (a steroid-requiring febrile illness without an infectious cause), and encephalitis, for all grades, and regardless of relationship to study drug. Additional medically important adverse events post-allogeneic SCT may be submitted at the Investigator's discretion. If available and relevant to an event post-allogeneic SCT, concomitant medications and/or laboratory results may also be reported.

4.6.4 Patient Replacement

Any patient who is registered to the study and then withdrawn without receiving any study treatment may be replaced. Any patient who completes fewer than 2 total cycles of therapy and is withdrawn for any reason except PD or toxicity will still be considered evaluable for toxicity endpoints; however, for the purpose of efficacy endpoints, another patient may be added; if the maximum accrual of 30 is reached without achieving the 26 evaluable necessary for evaluation of efficacy, an increase to the accrual goal may be requested with the approval of the Data and Safety Monitoring Committee (DSMC) at Northwestern University. No follow-up is required for patients that withdrew and did not receive any study treatment.

37

Initial Version date: March 10th, 2017

5.0 STUDY PROCEDURES

Trial Period:	Screening Phase	Treatment Cycles ¹							Off Rx	Surveillance		
		Pemb	orolizun	nab		AVD ^{2,3}		AVD ^{3,4}	Assessment	Pembrolizumab ⁵	Discont	Survival Follow-Up
Treatment Cycle/Title:	Main Study Screening	1	2	3	PET #2	1-2	PET #3	3-66	emo Asses	4-35		
Scheduling Window (Days):	Within 28 days of registration	1 ± 3	22 ± 3	43 ± 3		64 ± 3		120 ± 3	Post-Chemo	2-4 weeks after last dose of chemotherapy ± 3	30 days after last dose (pembro or AVD, ±5 days)	Every 12 weeks
Administrative Procedures												
Informed Consent	X											
Inclusion/Exclusion Criteria	X											
Demographics and Medical History	x											
Prior and Concomitant Medication Review	х	X	х	x		х		Х		X	X	
Trial Treatment Administration		X	X	X		X		X		X		
Post-study anticancer therapy status											X	X
Survival Status ⁷												X
Clinical Procedures/Assessments												
Review Adverse Events		X	X	X		X		X		X	X^{20}	X^{20}
Physical Examination	X	X	X	X		X		X		X	X	
Vital Signs ⁸ Weight and Height ²⁴	X	X	X	X		X		X		X	X	
ECOG Status ⁹	X	X	X	X		X		X		X	X	
Echocardiogram/MUGA	X							X^{21}				
Unfavorable risk factors/IPS ¹⁰	X											
Laboratory Procedures/Assessments: analysis performed by LOCAL laboratory												
Pregnancy Test – Urine or Serum β-HCG	x ²²	x ²²										
PT/INR and aPTT	Х											

Trial Period:	Screening Phase	Treatment Cycles ¹							Off Rx	Surveillance		
		Pemb	orolizun	nab		AVD ^{2,3}		AVD ^{3,4}	Assessment	Pembrolizumab ⁵	Discont	Survival Follow-Up
Treatment Cycle/Title:	Main Study Screening	1	2	3	PET #2	1-2	PET #3	3-6 ⁶		4-35		
Scheduling Window (Days):	Within 28 days of registration	1 ± 3	22 ± 3	43 ± 3		64 ± 3		120 ± 3	Post-Chemo	2-4 weeks after last dose of chemotherapy ± 3	30 days after last dose (pembro or AVD, ±5 days)	Every 12 weeks
CBC with ANC ¹¹	x ¹¹	X	X	X		x^3		\mathbf{x}^3		X	X	
Comprehensive Serum Chemistry Panel ¹¹	x ¹¹	X	Х	х		x^3		x^3		х	X	
Urinalysis	X											
T3, FT4 and TSH ¹²	X			Х						X		
ESR	X											
HIV, Hepatitis B, Hepatitis C ¹³	X											
Quantiferon-gold TB blood test ²⁵	x ²⁵											
Efficacy Measurements												
PET-CT ¹⁴	x ¹⁴				x ¹⁴		x ¹⁴		X ¹⁵	x ¹⁶	x ¹⁵	
CT scan ¹⁷	X									x ²³	X	
Tumor Biopsies/Archival Tissue Collection/Correlative Studies Blood performed by CENTRAL laboratory												
Archival or Newly Obtained Tissue Collection ¹⁸	X		x ¹⁸									
Correlative Studies Blood Collection ¹⁹		х				х					x	

- ¹⁴ PET/CT is required for eligibility within 6 weeks prior to registration (standard of care) and at specified time points for tumor assessment for the primary endpoint analysis. PET#2 should take place prior to starting AVD (research procedure). PET#3 should take place at the end of AVD Cycle 2 (standard of care). Copies of PET/CT scans should be de-identified and CD disks with DICOM files shipped within 30 days for central review as outlined in section 6.3.1.
- ¹⁵ All patients will have a PET/CT 2-6 weeks after the completion of chemotherapy (or diagnostic CT's for patients with Stage I/II disease and a negative PET#3) (standard of care). This will be prior to starting consolidation treatment (when applicable) or as part of the procedures for study discontinuation. Patients receiving consolidation will also have a final PET/CT as part of study discontinuation.
- ¹⁶ For patients who receive pembrolizumab consolidation, imaging is recommended every 3 months. Once a PET-CT is negative, patients may undergo CT's every three months during consolidation.
- ¹⁷ Diagnostic quality CT scan of the chest/abdomen/pelvis is required within 6 weeks prior to registration. If there is involvement of the neck then a diagnostic quality CT Neck is required.
- ¹⁸ Correlative studies on tissue specimens are recommended if there is adequate tissue on the baseline sample acquired for diagnosis. Patients who agree to undergo a repeat biopsy (optional: done as a research procedure) for the interim assessment will provide tissue 2-4 weeks after the first dose of pembrolizumab as specified in the lab manual, however repeat biopsy is not required.
- ¹⁹ See separate lab manual for details of correlative studies (research procedures). Study labs include:
 - (1) sodium heparin tube for FlowCore,
 - (2) SST tube for Inflammatory and Immune Markers,
 - (3) SST tube for Soluble PD-L1
 - (4) SST for CCL17

¹ Treatment cycle of pembrolizumab defined as 21 days, Treatment cycle of AVD defined as 28 days with treatment on days 1 and 15

² Interim assessment by FDG-PET #2 for primary endpoint assessment on day 64 +/- 3 days

³Labs including CBC w/ANC and comprehensive chemistry panel, physician visit with physical examination and vital signs to be performed on day 1 of each cycle of AVD.

⁴ Interim assessment by FDG-PET #3 for PET-directed therapy on day 117-120 prior to AVD cycle 3

⁵ Elderly patients may receive consolidation for a total of up to 1 or 2 years pembrolizumab treatment. Elderly patients who do not achieve CR after additional AVD will have pembrolizumab consolidation for up to 32 additional doses. Elderly patients with Stage III/IV disease who achieve CR after <6 cycles AVD will receive pembrolizumab consolidation for up to 14 additional doses. See section 4.2.3 for details.

⁶ See study schema in 1.2

⁷ Patients will be followed (either by routine clinic visit or by phone call) for survival every 12 weeks (±7 days) for 2 years from the last dose of study drug. Patients should also be monitored for occurrence of an allogeneic stem cell transplant within 24 months from the last study treatment. If patient undergoes an allo-SCT in this timeframe, transplant parameters and adverse events must be reported as specified in section 4.6.3 (up to 18 months from the time of SCT).

⁸ Vital Signs include: Blood pressure, pulse, respiratory rate, and oxygen saturation

⁹ See Appendix A

¹⁰ See Appendix D

¹¹ Comprehensive chemistry panel and CBC with differential are required within 14 days of study registration. Chemistry panel will include glucose, calcium, albumin, ALT, AST, sodium, potassium, total bilirubin, alk phose, and creatinine. CBC with differential must include Absolute Neutrophil Count.

¹² At baseline and every 6 weeks while on therapy with pembrolizumab.

¹³Patients must have HIV Ab screen; and Hepatitis B Sag, Sab, and core; and Hepatitis C Ab testing within 6 weeks of registration.

Trial Period:	Screening Phase	Treatment Cycles ¹						Off Rx	Surveillance			
		Pemb	orolizun	nab		AVD ^{2,3}		AVD ^{3,4}	sment	Pembrolizumab ⁵	Discont	Survival Follow-Up
Treatment Cycle/Title:	Main Study Screening	1	2	3	PET #2	1-2	PET #3	3-66	emo Asses	4-35		
Scheduling Window (Days):	Within 28 days of registration	1 ± 3	22 ± 3	43 ± 3	[64 ± 3	[120 ± 3	Post-Che	2-4 weeks after last dose of chemotherapy ± 3	30 days after last dose (pembro or AVD, ±5 days)	Every 12 weeks

²⁰ Adverse events will be followed for the first 30 days after treatment discontinuation. SAE's will be recorded for 90 days after treatment discontinuation. For patients who undergo allogeneic stem cell transplant (SCT) within 24 months of last study treatment, transplant parameters and adverse events will be recorded according to section 4.6.3 (up to 18 months from the time of SCT).

²¹ Echo or MUGA to be repeated after 4 cycles of doxorubicin

²² Pregnancy test (serum or urine) is required within 7 days of registration. Pregnancy test should also be repeated C1D1 if not done within 72 hours of study treatment.

²³ CT scans to be performed at baseline and every three months during pembrolizumab consolidation after PET-CT is negative (see footnote 14)

²⁴ Height required at baseline but not at subsequent visits

²⁵ Within 6 weeks prior to registration.

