- ж Patients with bulky disease (a mass >10 cm) at baseline and a negative PET #3 may receive 4-6 cycles of AVD per investigator discretion

[†]Biopsy in consenting patients and correlative studies to include: chromosome 9p24.1 alterations and PD-1 and PD-L1 expression

[‡]Correlative studies: Including flow cytometry, serum cytokines, and TARC

^{*}See Study Procedures for follow up. Patients with progressive disease will come off study.

[¢] escalated BEACOPP recommended but not required per protocol

 $^{^{\}Psi}$ Patients \geq age 60 unable to complete a total of 6 cycles of AVD chemotherapy due to poor tolerance

STUDY SUMMARY

Title	Phase II study of PET-directed frontline therapy with pembrolizumab and AVD for patients with classical Hodgkin lymphoma	
Version	March 29th, 2019 (Amendment 6)	
Study Design	This Phase II clinical trial will evaluate the use of pembrolizumab as frontline treatment of newly diagnosed Hodgkin lymphoma Stages I-IV followed by AVD. Patients will be treated with pembrolizumab at a flat dose of 200 mg every 3 weeks for 3 cycles followed by PET-CT to assess treatment response to pembrolizumab alone. Patients will then be treated with AVD chemotherapy for 4-6 cycles. Additional consolidation pembrolizumab will be given in elderly patients (≥ 60 years old) after chemotherapy who either:	
	 Have a Deauville score of 4 or 5 following interim PET-CT (PET #3; 32 additional doses), OR Have a Deauville score of 1-3 following interim PET-CT (PET#3) and receive less than the intended 6 cycles of AVD chemotherapy for stage III/IV disease because of poor tolerance (14 additional doses). 	
Study Center(s)	Robert H. Lurie Comprehensive Cancer Center Rutgers Cancer Institute of New Jersey Stanford University Medical Center Emory University	
Objectives		
Sample Size	Up to 30 patients; (for 26 evaluable) enrolling concurrently	

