Inclusion Criteria Histologically confirmed, classical Hodgkin lymphoma (cHL) Patients with Stage III and IV disease may have any International Prognostic Score (IPS) Patients with Stage I and II disease must have at least one NCCN unfavorable risk factor (see Appendix D) Age ≥18 Previously untreated disease (except for one week or less of Diagnosis & Key corticosteroids). **Eligibility Criteria** ECOG performance status 0, 1. Adequate organ and marrow function **Exclusion Criteria** Prior chemotherapy for cHL Concurrent active malignancy that is life-limiting Interstitial lung disease or idiopathic pulmonary fibrosis Uncontrolled intercurrent illness Active infection or autoimmune disease For all patients, PET-CT will be performed prior to treatment (PET#1). Treatment will commence with pembrolizumab at 200 mg, flat dosing, intravenously, every three weeks for three total doses, followed by restaging of disease with PET-CT (PET#2). All patients will then be treated with 2 cycles of AVD followed by PET#3. Subsequent therapy will then be based on age, stage, and results of this PET-CT (PET#3). Younger patients (<60 years old): Stage I/II: Those with negative PET#3 (DV Score 1-3) proceed to 2 additional cycles of AVD (4 cycles permissable for bulky masses per investigator discretion) For those with a Deauville Score (DV) of 4-5, it is recommended that they receive 2 cycles of escBEACOPP +/- RT at investigator discretion. Stage III/IV: Patients with negative PET#3 (DV Score of 1-3) will receive 4 cycles of AVD as tolerated to complete a total of 6 cycles of AVD. It is recommended that those with a Deauville Score (DV) of 4-5 receive 4 cycles of escBEACOPP +/- RT at **Treatment Plan** investigator discretion. Elderly patients (≥60 years old): Stage I/II: Following PET#3, all patients will receive 2 additional cycles of AVD (4 total cycles) regardless of Deauville score with the option for 4 additional cycles or six total for those with bulky disease, per investigator discretion. Those with Deauville 1, 2, or 3 (PET#3) will then continue to followup. Those with Deauville 4 or 5, should receive consolidation treatment with pembrolizumab for 2 years total (3 doses in induction + 32 doses in consolidation).

Initial Version date: March 10th, 2017 Amendment 6: March 29th, 2019

Stage III/IV: Following PET#3, all patients will receive 4 additional cycles of AVD (6 total cycles) regardless of Deauville score. Those with Deauville 4 or 5 (PET#3) should receive

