4.2.3 Pembrolizumab Consolidation

Patients who are ≥60 may receive pembrolizumab consolidation (either 14 or 32 additional doses) if they fall into the categories below:

- Elderly patients with any stage disease with a positive PET #3 (Deauville 4, 5) will proceed to pembrolizumab consolidation at a dose of 200mg IV flat dose every 21 days for 2 years total treatment (3 induction doses + 32 consolidation doses).
- Patients with stage III/IV disease with a negative PET #3 who receive <
 the planned 6 cycles of AVD therapy will proceed to pembrolizumab
 consolidation at a dose of 200mg IV flat dose every 21 days for up to 1
 year total treatment (3 induction doses + 14 consolidation doses).
- In patients receiving consolidation therapy, pembrolizumab should commence 4 weeks after day 1 of the final cycle of AVD. For patients in remission having received fewer than six full cycles of AVD, patients may be followed with CT scans every three months during consolidation. For other patients receiving consolidation, PET/CT is recommended every 3 months during consolidation therapy until negative. Once PET-CT is negative, CT's should be obtained every three months during consolidation.

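### Schedule footnote 5 assigns pembrolizumab consolidation by response after AVD, whereas section 4.2.3, the study summary and the overview assign it by PET#3

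*Combined protocol and SAP*

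**What the plan says.** **Schedule of procedures (section 5.0), footnote 5.** For 32 doses: "Elderly patients who do not achieve CR after additional AVD will have pembrolizumab consolidation for up to 32 additional doses". For 14 doses: "Elderly patients with Stage III/IV disease who achieve CR after <6 cycles AVD will receive pembrolizumab consolidation for up to 14 additional doses". The footnote then refers the reader to 4.2.3 for details. Neither sentence mentions PET#3.

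**Same schedule, footnote 4.** "Interim assessment by FDG-PET #3 for PET-directed therapy on day 117-120 prior to AVD cycle 3".

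**Section 4.2.3, for patients aged 60 or older.** For 32 doses: "Elderly patients with any stage disease with a positive PET #3 (Deauville 4, 5) will proceed to pembrolizumab consolidation". For 14 doses, the rule covers stage III/IV patients with a negative PET#3 who get fewer than "the planned 6 cycles of AVD therapy will proceed to pembrolizumab" consolidation.

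**Study Summary.** Under Study Design, the 32-dose group are those who "Have a Deauville score of 4 or 5 following interim PET-CT (PET #3; 32 additional doses"). The 14-dose group have Deauville 1-3 at PET#3 and "receive less than the intended 6 cycles of AVD chemotherapy for stage III/IV disease because of poor tolerance". Under Treatment Plan, for older stage I/II patients: "Those with Deauville 4 or 5, should receive consolidation treatment with pembrolizumab for 2 years total". The stage III/IV text there uses PET#3 in the same way.

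**Section 4.1 (overview).** A positive PET#3 is one trigger; advanced stage with fewer than 6 AVD cycles because of poor tolerance is the other.

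**The concern.** The two rules rest on different assessments at different times. PET#3 is read after two AVD cycles. CR after additional AVD can only be read on the imaging that follows chemotherapy (section 4.2.2.2.3). Patients aged 60 or older with a positive PET#3 continue AVD to 4-6 cycles in total (section 4.2.2.2.2), so some may convert to CR. They must have PET#4 before consolidation starts, so the site sees that CR just when it has to decide on consolidation.

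A site working from the schedule could then withhold pembrolizumab that 4.2.3 assigns or, less likely, give it where 4.2.3 assigns none. Section 11.6 requires the study to be run as the protocol describes, yet for such a patient no course satisfies both texts. The exposure at stake is long and carries mandatory hold and discontinuation rules (Table 4.1). Safety is summarised by age cohort (10.3.2), and response, PFS and OS are also analysed by age cohort (10.2), so misassignment would fall within one reported group.

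**Working it through.** **Inputs.** Dosing every 21 days; 32 or 14 consolidation doses (4.2.3). AVD cycle 1 on day 64; 28-day cycles with doses on days 1 and 15; PET#3 on day 117-120; AVD cycle 3 on day 120 (4.2.2.1 and 5.0). Post-chemotherapy imaging 2-6 weeks after chemotherapy (4.2.2.2.3).

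**Duration.** 32 × 3 = 96 weeks, which reproduces the maximum consolidation length in the Study Summary. 14 × 3 = 42 weeks. The difference is 18 × 3 = 54 weeks.

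**Gap between the two assessments** (no delays; completion counted from the last AVD dose).
- Two further cycles: cycle 4 starts day 148; last dose 148 + 14 = day 162; imaging day 176-204. Gap from 176 − 120 = 56 to 204 − 117 = 87 days, about 8-12 weeks.
- Four further cycles: cycle 6 starts day 204; last dose 204 + 14 = day 218; imaging day 232-260. Gap from 232 − 120 = 112 to 260 − 117 = 143 days, about 16-20 weeks.

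**The two rules side by side**, age 60 or older, no progression. (Progression takes a patient off study under the schema note and 4.6.3.)

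| PET#3 | After AVD | Stage and cycles | 4.2.3 | Footnote 5 | Difference |
|---|---|---|---|---|---|
| Positive | Not CR | Any | 32 | up to 32 | none |
| Positive | CR | I/II, or III/IV with 6 cycles | 32 | 0 | 32 doses, 96 weeks |
| Positive | CR | III/IV, fewer than 6 | 32 | up to 14 | 18 doses, 54 weeks |
| Negative | CR | I/II, or III/IV with 6 cycles | 0 | 0 | none |
| Negative | CR | III/IV, fewer than 6 | up to 14 | up to 14 | none |
| Negative | Not CR | I/II, or III/IV with 6 cycles | 0 | up to 32 | up to 32 doses |
| Negative | PR | III/IV, fewer than 6 | up to 14 | up to 32 | up to 18 doses |

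The rules agree when the two assessments agree and conflict when they do not. Section 4.3.2 lets chemotherapy-intolerant patients proceed to consolidation only in PR or CR. Both positive-then-CR rows end in CR, so that condition does not resolve them.

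The negative-then-not-CR rows are less likely but possible. A stage I/II patient with a negative PET#3 may have only a CT after chemotherapy (4.2.2.2.3). Appendix C requires nodes below 1.5 cm for CR by CT, while CR by PET allows a residual mass.

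**The case against.** The strongest reply is that the protocol already settles the matter. Footnote 5 opens permissively and ends by sending the reader to 4.2.3, which is the treatment section. The summary and overview also use PET#3. For the reverse case, the summary explicitly sends PET#3-negative older patients to follow-up if they have stage I/II disease or have completed 6 cycles. Harm needs an older patient, discordant assessments and a site that does not follow the pointer. PFS and OS are descriptive Kaplan-Meier estimates with no test of consolidation.

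Most of this stands. It shows that the governing rule can be recovered and that the consequence is limited. It does not make the footnote correct. A pointer to details adds to a rule; it does not reverse one, and the footnote's two sentences are worded as directives. Section 4.2.3 also opens permissively before giving its directives, so that feature does not separate the two texts.

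A reader might infer that the consolidation rule is undefined. The documents do not support that: three places and footnote 4 agree on PET#3. A reader might also blame superseded text in the summary of changes. That is not the basis here, since both conflicting texts are in the current protocol body.

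**Conclusion.** Footnote 5 is wrong as written: an internal inconsistency in a treatment rule, worth correcting. In the main case, Deauville 4-5 at PET#3 followed by CR, the texts differ by 32 doses (96 weeks), or by 18 doses (54 weeks) in stage III/IV with fewer than 6 AVD cycles, taking the 14-dose course in full. The reverse discordance carries little weight.

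It would be tempting to conclude that the trial's main result is compromised. It is not. The primary endpoint is CR at PET#2, before any AVD, so the endpoint, sample size and power are untouched. What can change is consolidation exposure, safety and descriptive PFS and OS in patients aged 60 or older.

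The documents give neither the number of patients aged 60 or older nor their PET#3-positive rate, so I estimate no count. Total accrual is planned at up to 30. The dose differences assume on-schedule dosing and no progression.

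**What to change.** Replace the two assignment sentences of footnote 5 with:

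> Age ≥60, any stage, PET#3 Deauville 4-5: 32 consolidation doses. Age ≥60, stage III/IV, PET#3 Deauville 1-3, fewer than the planned 6 AVD cycles: up to 14 consolidation doses. See section 4.2.3, and section 4.3.2 for the PR/CR condition in chemotherapy-intolerant patients.

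Send sites a short notice of the change.

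Optional harmonisation: the schema note, summary and overview tie the 14-dose course to poor tolerance of AVD, while 4.2.3 and footnote 5 do not. If that condition is intended, add it to both. This is secondary, because 4.2.2.2.1 already links the number of cycles to tolerability and 4.3.2 describes chemotherapy intolerance.

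Cost: a wording amendment to one footnote, a few words in 4.2.3 if the tolerance condition is kept, and the site notice. Sample size, primary endpoint and visit schedule stay as they are.
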